
## 20.2.4. Selection and Withdrawal Criteria of Subjects for the OLE Phase

### 20.2.4.1. Inclusion Criteria

A subject is eligible for enrollment into the COLE phase of this study if he/she meets the following criteria:

- Has completed the randomization phase and open label phase through Visit 6 (Study Day 84);
- Is willing to provide an additional written informed consent for the COLE phase if enrolled in study prior to COLE becoming available.

See [Section 6.1](#) for complete study Inclusion Criteria and [Section 6.2](#) for complete study Exclusion Criteria.

### 20.2.4.2. Early Withdrawal of Subjects

The term “discontinuation” refers to the subject’s premature withdrawal from the study before completing all scheduled evaluations.

Subjects may voluntarily withdraw from the COLE at any time for any reason. Subjects may also be discontinued from the study for any of the following reasons:

- If in the Investigator’s judgment, continuation in the study may prove harmful to the subject. Such a decision may be precipitated by adverse events, including changes in vital signs, physical examination, ECG, or laboratory tests. The Investigator will maintain autonomy in making medical/safety decisions regarding the subject’s continued participation in the trial. Clinically notable abnormalities in vital signs or laboratory tests are provided in [Appendices 20.4](#) and [20.3](#), respectively, to guide clinical focus regarding a subject’s continued participation;
- Noncompliance;

For subjects withdrawing from the study prematurely, all efforts will be made to perform the COLE Visit 7 Early Termination procedures.

Documented reason:

It will be documented whether or not each subject completed the clinical study. If, for any subject, study treatment or observations were discontinued, the reason will be recorded (only 1 choice is acceptable) on the electronic case report form (electronic CRF). Acceptable reasons for a subject discontinuing participation in this clinical study are as follows:

9. Protocol deviation (including noncompliance to study requirements)
10. Adverse event(s) (including abnormal laboratory values, and abnormal test procedures)
11. Pregnancy
12. Lost to follow-up
13. Death
14. Subject withdrew consent
15. Unsatisfactory therapeutic effect
16. Other (specify).

**20.2.5. Treatment of Subjects**

**20.2.5.1. Dosing**

Subjects will be dispensed study medication under open-label conditions at the study visits indicated in the Schedule of Evaluations for COLE ([Table 9](#)). Subjects will be instructed to take one capsule of study medication every day in the morning, and one capsule of study medication every day in the evening approximately 12 hours later. Each capsule will contain either 85 mg of tradipitant.

**20.2.5.2. Guidance for Taking Study Medication**

Subjects should be instructed to take study medication approximately every 12 hours at the same times each day. The morning dose of study medication should be taken at least 30 minutes

before breakfast and the evening dose of study medication should be taken at least 30 minutes prior to dinner or bedtime. Study medication should be taken on an empty stomach whenever possible.

In the event that a patient vomits within 15 minutes of taking study medication and an intact capsule can be identified in the emesis, a second capsule should be administered.

#### **20.2.6. Concomitant Medication During the COLE Phase**

The administration of concomitant medication (including OTC medication) will be clearly documented on the concomitant medication CRF page.

In general, concomitant medications that may interfere with the assessment of the efficacy and safety of tradipitant are not allowed in this protocol or are allowed with specific provisions.

##### **20.2.6.1. Prohibited Medication**

Prohibited medications and treatments are prohibited from the screening visit (or 4 weeks prior to the Randomization Visit when a washout is required) through the end of study participation. Questions regarding the use of concomitant medications not listed should be directed to the Medical Monitor.

All medications prohibited during the randomization phases ([Section 7.2.1](#)) will also be prohibited during this phase.

##### **20.2.6.2. Rescue Medication**

Anti-nausea or antiemetic medication that is not administered on a stable daily dosing regimen is considered rescue medication. Patients may use rescue medication per the Rescue Medication Guidelines ([Section 7.2.2.1](#)).

#### **20.2.7. Treatment Compliance**

Compliance in this study will be assessed by the Investigator. The Investigator will consider patient interviews as well as returned capsules when assessing compliance. Subjects who were not fully compliant will be re-educated by the Investigator or study staff on the importance of taking the study medication daily at the scheduled time.

Any overdose that occurs during study participation must be recorded on the overdose CRF. An overdose (intentional or accidental) is defined as the following: >3 capsules of open label study medication taken within a 24-hour period (except when re-administered within the guidance of [Section 7.1.2](#)).

### **20.2.8. Treatment Assignment**

At COLE Visits 1-6, ([Table 9](#)), study personnel will dispense enough COLE medication to the subject to last until the next scheduled visit.

### **20.2.9. Study Drug, Packaging, and Labeling**

[REDACTED]

[REDACTED]

Study medication should be stored at 20-25 °C with excursions permitted to 15-30 °C. Capsules should not be crushed or broken, but should be swallowed whole. Study medication will be dispensed to only randomized subjects at the study site.

### **20.2.10. Study Medication Materials and Management**

See [Section 8](#) for information on study medication packaging, storage and accountability.

### **20.2.11. Study Assessments per Visit**

#### **20.2.11.1. COLE Screening Visit A or B (Visit 1, COLE Day 0)**

The following will be performed after the subject signs the informed consent form:

- Review of inclusion/exclusion criteria
- Collection of demographic information, medical history, and prior and concurrent medications;
- Vital sign and body measurements
- Patients who are coming directly from VP-VLY-686-2301 Visit 6 can coordinate this visit with VP-VLY-686-2301 Visit 6.
- Patients who are returning after a gap (Visit 1-B) will perform the following additional procedures:
  - Physical examination (PE) (excluding pelvic, rectal and breast examinations unless clinically indicated)

- ECG
- Screening C-SSRS questionnaire
- Clinical laboratory assessments: hematology, chemistry (including estimated creatinine clearance (eCLcr; based on the Cockcroft-Gault equation), urinalysis, HbA1c, thyroid stimulating hormone (TSH), thyroxine (T4), urine drug screen,
- Serum pregnancy test and collection of menstrual cycle information (for females of child-bearing potential)
- Modified Gastroparesis Cardinal Symptom Index (mGCSI) Part I
- Modified PAGI-SYM (mPAGI-SYM)
- Gastroparesis Treatment Benefit Survey (GTBS)
- Study medication instruction and dispensation

Collection of adverse event information will begin at the time the ICF is signed. Subjects will be set up on phone diary and instructed to begin completing their diary daily ([Section 10.1.1](#)).

**20.2.11.2. COLE Visit 2-Visit 6 (COLE Day 28, Day 84, Day 140, Day 196, Day 280, ± 5 days)**

On COLE Visit 2 through Visit 6, the following assessments will be performed to assess the subject's continued eligibility:

- Adverse Event query
- Concomitant medication review
- Urine pregnancy test (for females of child-bearing potential)
- Semi-supine routine vital signs (body temperature, respiratory rate, blood pressure, and pulse)
- ECG
- Physical examination (PE) (excluding pelvic, rectal and breast examinations unless clinically indicated)
- Clinical laboratory assessments (HbA1C, hematology, chemistry (including eCLcr; based on the Cockcroft-Gault equation), urinalysis, thyroid stimulating hormone (TSH), thyroxine (T4), and urine drug screen)
- Since last visit C-SSRS
- Diary review
- Modified Gastroparesis Cardinal Symptom Index (mGCSI)
- Modified PAGI-SYM (mPAGI-SYM)
- Patient Global Impression of Change (PGI-C)

- Clinical Global Impression of Severity (CGI-S)
- Study medication collection and review
- Study medication dispensation
- Schedule Monthly Calls

**20.2.11.3. COLE Visit 7/End of Study/Early Termination (COLE Day 365, ± 7 days)**

- Adverse Event query
- Concomitant medication review
- Full PE (excluding pelvic, rectal and breast examinations unless clinically indicated)
- Laboratory evaluations (HbA1C, hematology, chemistry (including eCLcr; based on the Cockcroft-Gault equation), urinalysis, thyroid stimulating hormone (TSH), thyroxine (T4), and urine drug screen)
- Serum pregnancy test and collection of menstrual cycle information (for females of child-bearing potential)
- ECG
- Semi-supine routine vital signs (body temperature, respiratory rate, blood pressure, and pulse) and weight
- Since last visit C-SSRS
- Diary review
- Modified Gastroparesis Cardinal Symptom Index (mGCSI)
- Modified PAGI-SYM (mPAGI-SYM)
- Patient Global Impression of Change (PGI-C)
- Patient Assessment of Upper Gastrointestinal Disorder Quality of Life (PAGI-QOL)
- Clinical Global Impression of Severity (CGI-S)
- Study medication collection and review
- Record EOS

**20.2.11.4. Unscheduled Visits**

Unscheduled visits may be performed at any time at the discretion of the Investigator.

#### **20.2.11.5. Monthly Calls to Patients (COLE Day 56, Day 112, Day 224, Day 252, Day 308, Day 336, ± 3 days)**

Members of the study team will call patients between visits to assess overall health and query for any adverse events or updates to their current medication. An unscheduled visit will be performed if medically warranted in the opinion of the Investigator.

#### **20.2.12. Efficacy Assessments**

The efficacy assessments should be conducted as specified in the Schedule of Evaluations for COLE ([Table 9](#)). These assessments include: the Gastroparesis Core Symptom Daily Diary (GCSDDD), Modified Gastroparesis Cardinal Symptom Index (mGCSI), Modified PAGI-SYM (mPAGI-SYM), Patient Global Impression of Change (PGI-C), and the Patient Assessment of Upper Gastrointestinal Disorders-QOL (PAGI-QOL) (see [Section 10.1.1](#) for a description of the patient reported outcomes) and the Clinician Global Impression – Severity (CGI-S) (see [Section 10](#) for complete descriptions of the assessments).

#### **20.2.13. Safety Assessments**

The safety assessments should be conducted as specified in the Schedule of Evaluations for COLE ([Table 9](#)). These assessments include: the regular monitoring and recording of all adverse events and serious adverse events (SAEs); the regular monitoring of hematology, blood biochemistry and urinalysis values; the regular monitoring of vital signs; the regular monitoring of suicidal ideation and behavior, and the performance of physical examinations, and electrocardiograms.

Refer to [Section 11](#) for additional details relating to the collection of safety assessments and adverse event reporting.

#### **20.2.14. Statistical Methods**

Statistical analysis for the COLE phase will be based on data summaries, using similar layouts as for the randomization phase, and will be exploratory in nature (See [Section 13](#) for further details).

### **20.3. Laboratory Ranges Used to Identify Clinically Notable Abnormal Laboratory Values**

Criteria for identifying laboratory values as Potentially Clinically Notable Abnormalities are based on the Guidelines for the Division of Neuropharmacological Drug Products, US Food and Drug Administration (revised on April 2, 1987).

Variable	Criterion Values	
	Standard Units	SI Units
Chemistry		
SGOT	≥ 3 x Upper Limit Normal	
SGPT	≥ 3 x Upper Limit Normal	
Alkaline Phosphatase	≥ 3 x Upper Limit Normal	
LDH	≥ 3 x Upper Limit Normal	
BUN	≥ 30 mg/dL	≥ 10.7 μM
Creatinine	≥ 2.0 mg/dL	≥ 176.8 μM
Uric Acid	Male ≥ 10.5 mg/dL	≥ 624.6 μM
	Female ≥ 8.5 mg/dL	≥ 505.6 μM
Bilirubin (Total)	≥ 2.0 mg/dL	≥ 34.2 μM
Hematology		
Hematocrit	Male ≤ 37%	
	Female ≤ 32%	
Hemoglobin	Male ≤ 11.5 g/dL	
	Female ≤ 9.5 g/dL	
Platelets	≤ 75,000/mm  or ≥ 700,000/mm 	≤ 75 x 10  /L or ≥ 700 x 10  /L
Leukocytes	≤ 2,800/mm  or ≥ 16,000/mm 	≤ 2.8 x 10  /L or ≥ 16 x 10  /L
Eosinophils	≥ 10%	
Neutrophils	≤ 15%	
Urinalysis		
Protein	Increase of ≥ 2 units	
Glucose	Increase of ≥ 2 units	
Casts	Increase of ≥ 2 units	

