### 6.3. Subject Withdrawal Criteria

The term “discontinuation” refers to the randomized subject’s premature withdrawal from the study before completing all scheduled evaluations.

Subjects may voluntarily withdraw from the study at any time for any reason. Subjects may also be discontinued from the study for any of the following reasons:

- If in the Investigator’s judgment, continuation in the study may prove harmful to the subject. Such a decision may be precipitated by adverse events, including changes in vital signs, physical examination, ECG, or laboratory tests. The Investigator will maintain autonomy in making medical/safety decisions regarding the subject’s continued participation in the trial. Clinically notable abnormalities in vital signs or laboratory tests are provided in [Appendices Section 20.4](#) and [Section 20.3](#), respectively, to guide clinical focus regarding a subject’s continued participation;
- Noncompliance;

For subjects withdrawing from the study prematurely, all efforts will be made to perform the Visit 4 Early Termination procedures.

Documented reason: It will be documented whether or not each subject completed the clinical study. For subjects who do not complete the clinical study, the primary reason for discontinuation will be documented in the CRF. Possible reasons for discontinuation include:

1. Protocol deviation (including noncompliance to study requirements)

2. Adverse event(s) (including abnormal laboratory values, and abnormal test procedures)
3. Pregnancy
4. Lost to follow-up
5. Death
6. Subject withdrew consent
7. Unsatisfactory therapeutic effect
8. Other (specify).

Subjects who discontinue because of an AE, abnormal laboratory value, or abnormal test result will be followed until resolution or for 30 days, whichever is less. Events which are stable after 30 days will not require additional follow up.

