#### 11.1.2. Laboratory Evaluations

The Schedule of Evaluations ([Table 3](#)) shows the days at which blood will be collected for clinical laboratory tests and urine for the urinalysis.

The table below, [Table 5](#), presents the clinical laboratory tests to be performed.

Clinical laboratory tests will be performed by a certified laboratory that will forward laboratory data to both the site and Vanda or its designee.

Values considered to be potentially clinically notable are provided in [Appendix 20.3](#) for the Investigator's guidance. Any laboratory test result from an enrolled subject that the Investigator considers clinically significant may be repeated once to rule out laboratory error. For tests where a persistent abnormality is considered to be drug related, repeat analyses will be performed until the cause is determined and either a return to normality occurs or the Investigator deems the abnormality to be of no clinical significance. Any laboratory test result that the Investigator considers clinically significant must also be recorded as an adverse event.

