**Table 5: Clinical Laboratory Tests**

Category	Parameters
Hematology	Red blood cell count (RBC), hemoglobin, hematocrit, platelets, and white blood cell (WBC) count with differential (neutrophils, lymphocytes, monocytes, eosinophils, basophils)
Chemistry	

Category	Parameters
Electrolytes	sodium, potassium, chloride, magnesium, bicarbonate
Liver function test	alkaline phosphatase, aspartate aminotransferase (AST [SGOT]), alanine aminotransferase (ALT [SGPT]), total bilirubin, gamma-glutamyltransferase (GGT)
Renal function parameters	blood urea/blood urea nitrogen (BUN), creatinine, eCLcr
Other	glucose, calcium, albumin, total cholesterol, high density lipoprotein (HDL), low density lipoprotein (LDL), triglycerides, phosphorus, lactate dehydrogenase (LDH), total protein, uric acid, creatine kinase
Urinalysis	
Gross and chemical exam	color, appearance, specific gravity, pH, protein, glucose, ketone, blood, nitrite
Reflexive microscopic exam (will be done if any of the urinalysis testing is not negative)	RBC, WBC, epithelial cells, bacteria, casts, crystals

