### **13.4. Safety Data Analysis**

The primary assessment of safety will be based on the frequency of treatment-emergent adverse events (TEAEs), serious adverse events (SAEs) and on the frequency of clinically notable abnormal vital signs, electrocardiograms (ECGs) and laboratory values. Other safety evaluations include changes in vital signs, changes in clinical laboratory evaluations, and changes in ECGs, physical exam findings during treatment, and suicide ideation and behavior events.

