### 13.4.2. Laboratory Data

#### **Clinical Laboratory Data**

The summary statistics of raw data (hematology and chemistry) and change from baseline values will be presented, as well as shift tables from baseline to post-baseline values using normal ranges. For urinalysis parameters, the number and percentage of subjects falling under each category of the test will be presented.

Clinical laboratory data will be summarized for each treatment group by presenting the proportions of subjects with clinically notable abnormalities ([Appendix 20](#)).

Clinically notable values will be identified according to the criteria identified in the FDA's "Supplementary Suggestions for Preparing an Integrated Summary of Safety Information in an Original NDA Submission and for Organizing Information in Periodic Safety Updates" (Revised 2-APR-87) provided by the FDA Division of Neuropharmacological Drug Products (DNDDP). Differences in incidence rates between the treatment groups will be tested as described in the SAP.

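### Section 20.3: the two unit columns of the BUN criterion differ by a factor of 1000 (μM printed where the number fits mmol/L)

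*Combined protocol and SAP*

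**What the plan says.** Section 20.3 is introduced by the sentence beginning "Criteria for identifying laboratory values as Potentially Clinically Notable Abnormalities are based on the Guidelines" and attributes its limits to a 1987 FDA divisional guideline. Its table has one row per analyte and two columns, standard units and SI units. The BUN row reads ≥ 30 mg/dL in the first and ≥ 10.7 μM in the second. Four other entries are also in μM: creatinine, uric acid for men, uric acid for women, and total bilirubin.

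The limits are used in two ways.

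- **Analysis.** Section 13.4 rests the main safety assessment partly "on the frequency of clinically notable abnormal vital signs, electrocardiograms (ECGs) and laboratory values". Section 13.4.2 adds: "Clinical laboratory data will be summarized for each treatment group by presenting the proportions of subjects with clinically notable abnormalities". It also says that differences in incidence between arms will be tested as the SAP describes.
- **Individual subjects.** Section 11.1.2 offers the limits to the investigator as guidance ("Values considered to be potentially clinically notable are provided in" the appendix). Section 6.3 cites them in connection with whether a subject continues ("Clinically notable abnormalities in vital signs or laboratory tests are provided in" the appendices), and Section 20.2.4.2 does the same for the 52-week extension.

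BUN is among the tests collected. The renal line of Table 5 reads "blood urea/blood urea nitrogen (BUN), creatinine, eCLcr". The visible text does not say which unit system will drive the flags.

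**The concern.** Two columns of one row should state the same limit in different units. In the BUN row they do not, and the gap is three orders of magnitude. The table is operative text: it decides which values count towards a rate that Section 13.4.2 reports by arm, and it is handed to investigators.

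If a programmer took the SI limit as printed and applied it to values expressed in μM, the BUN flag would be met by anyone with a measurable BUN. The rate would then be essentially 100% in each arm, and a comparison of the arms on that flag would carry no information. What is at stake is one safety flag for one analyte.

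**Working it through.** **Inputs from Section 20.3.** BUN 30 mg/dL and 10.7 μM; creatinine 2.0 mg/dL and 176.8 μM; uric acid 10.5 mg/dL and 624.6 μM (men), 8.5 mg/dL and 505.6 μM (women); total bilirubin 2.0 mg/dL and 34.2 μM.

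**Assumed constants.** The documents give no molar masses. I used, in g/mol: urea nitrogen 28.014 (two nitrogen atoms), creatinine 113.12, uric acid 168.11, bilirubin 584.66. As a variant reading of the BUN row, whole urea is 60.056.

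**Formula.** μmol/L = (mg/dL × 10 ÷ molar mass) × 1000. The factor 10 turns mg/dL into mg/L.

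**Step 1: reproduce the plan's other μM entries.**

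| Row | Calculation | Result (μM) | Printed (μM) |
|---|---|---|---|
| Creatinine | 20 ÷ 113.12 × 1000 | 176.8 | 176.8 |
| Uric acid, men | 105 ÷ 168.11 × 1000 | 624.6 | 624.6 |
| Uric acid, women | 85 ÷ 168.11 × 1000 | 505.6 | 505.6 |
| Bilirubin | 20 ÷ 584.66 × 1000 | 34.2 | 34.2 |

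All four agree, so the formula matches how the column was built.

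**Step 2: the BUN row.** 300 ÷ 28.014 = 10.709 mmol/L, which is 10,709 μM. The printed entry is 10.7 μM. The ratio is 10,709 ÷ 10.7 ≈ 1,001, that is, a factor of 1000 after rounding. The digits 10.7 are right with the unit mmol/L and wrong with μM.

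**Step 3: does reading the row as whole urea rescue it?** 300 ÷ 60.056 = 4.995 mmol/L, or 4,995 μM. Neither figure is 10.7, so it does not.

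**Step 4: read the printed SI limit back.** 10.7 μM is 0.0107 mmol/L. 0.0107 × 28.014 ÷ 10 = 0.030 mg/dL of urea nitrogen (0.064 mg/dL if read as whole urea).

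**Step 5: what each way of flagging would do.**

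- *mg/dL data against 30 mg/dL:* works as stated in the standard column.
- *mmol/L data against the bare number 10.7:* works. The limit is then 10.7 × 28.014 ÷ 10 = 29.97 mg/dL, the stated 30 to rounding.
- *μM data against 10.7 μM:* fails. A BUN of only 1 mg/dL is 10 ÷ 28.014 × 1000 = 357 μM. For ordinary values, which I assume to lie between 7 and 20 mg/dL, the range is 2,499 to 7,139 μM. Every such subject exceeds the limit.

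Only the third route does harm.

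**The case against.** The conversion itself is hard to dispute. The case on the other side concerns the consequence, and most of it stands.

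**Would every subject be flagged?** A reader might infer this from the row. The documents do not support it as a prediction. Nothing says that flags will be run on the SI column, still less on values in μM. The trial is run only in the United States (Section 5.1) and the table lists mg/dL first, so flags on mg/dL data are plausible. Laboratory data in mmol/L compared with 10.7 would also be flagged as intended.

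**Would real BUN changes be hidden?** A reader might infer this too. Section 13.4.2 rules it out: it also plans summaries of raw chemistry values, changes from baseline, and shift tables based on normal ranges, none of which uses the Section 20.3 limit. A flag rate of 100% in both arms would also be conspicuous at table review.

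**Would investigators be misled?** Sections 6.3 and 11.1.2 present the limits as guidance and leave the judgement with the investigator. No discontinuation is triggered by this row alone.

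**Is the table the only source?** No. Section 13.4.2 also names the FDA criteria directly, and Section 13.2 leaves the full methods to the SAP. No programming specification is visible, so whether the label has been carried forward is unknown.

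**Could the symbol be a reading error from the PDF?** The point turns on one character, so this cannot be excluded. Against it, the row is otherwise intact and the same symbol is right in the four other entries. A look at the source page settles it.

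What remains is the internal contradiction in the row, which none of these arguments removes.

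**Conclusion.** The point holds as a unit inconsistency. In Section 20.3 the two columns of the BUN row contradict each other by a factor of 1000, and BUN is the only one of the five μM entries that fails to convert. This rests on standard molar masses, which the documents do not give, and on the symbol having been read correctly from the page.

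The practical effect is conditional and small. The BUN rate in Section 13.4.2 becomes uninformative only if the SI limit is applied literally to values in μM. Under the other two routes no result changes. The primary efficacy analysis and the rest of the laboratory analysis are untouched. It is a minor correction, worth making because the table supplies limits for a reported safety rate and the remedy costs almost nothing.

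**What to change.** Reconcile the two columns of the BUN row in Section 20.3. The arithmetic equivalent of the stated 30 mg/dL is 10.7 mmol/L. This concerns agreement between the columns and takes no view on what the limit should be.

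Then confirm, in the SAP or wherever the flags are derived, which unit system is used for BUN and that the limit and the data are in the same unit.

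The cost is one unit label in the appendix and a short check of any derivation that uses the table. No data collection, sample size or efficacy analysis changes.

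### Notable neutrophils and eosinophils are defined only as percentages, so the flag depends on the white count and can order absolute counts backwards; add absolute-count rows to the analysis

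*Combined protocol and SAP*

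**What the plan says.** The hematology part of the section 20.3 table has three rows that matter here. The differential rows read "Neutrophils ≤ 15" and "Eosinophils ≥ 10", both in percent, with the SI column empty. The leukocyte row is an absolute count, "≤ 2,800/mm 3 or ≥ 16,000/mm 3", and platelets are also given as counts. The section states the source of the limits: "Criteria for identifying laboratory values as Potentially Clinically Notable Abnormalities are based on the Guidelines for the Division of Neuropharmacological Drug Products".

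Table 5 shows where the two percentages come from. The hematology panel includes a "white blood cell (WBC) count with differential (neutrophils, lymphocytes, monocytes, eosinophils, basophils"), so both cell types are measured as part of the white-cell differential.

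The limits are used in three places:
- Section 13.4 bases the primary assessment of safety partly "on the frequency of clinically notable abnormal vital signs, electrocardiograms (ECGs) and laboratory values".
- Section 13.4.2 summarizes laboratory data for each arm by "presenting the proportions of subjects with clinically notable abnormalities", and leaves the between-arm test of those rates to the SAP.
- Sections 6.3 and 20.2.4.2 refer the investigator to the same table when continued participation is considered: "Clinically notable abnormalities in vital signs or laboratory tests are provided in" the appendices.

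No section of the document gives an absolute neutrophil or eosinophil limit.

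**The concern.** A percentage of the white count is a ratio, so it can move because the numerator changes or because the denominator does. Two subjects with the same neutrophil percentage can have very different neutrophil counts, and two with the same count can fall on opposite sides of the limit. The leukocyte row limits this at both ends, but white counts between 2,800 and 16,000/mm³ remain open, and that is nearly a six-fold span (16,000 / 2,800 = 5.7).

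What is at stake is the content of one safety table. If a drug effect appeared as a fall in absolute neutrophils or a rise in absolute eosinophils, the notable-value proportions could classify some subjects in the wrong order. Those proportions are a named component of the primary safety assessment.

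**Working it through.** **Inputs.** Section 20.3: neutrophil row fires at ≤ 15%; eosinophil row fires at ≥ 10%; leukocyte row fires at ≤ 2,800 or ≥ 16,000/mm³. The denominator is taken to be the white count. The table does not name it; this is inferred from the differential in Table 5. The plan states no absolute count for either cell, so there is no figure of its own to reproduce.

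**Formula.** Absolute count = white count × percentage / 100.

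**Neutrophils, with both rows applied together.**

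| White count (/mm³) | Neutrophils (%) | Absolute count (/mm³) | Neutrophil row | Leukocyte row |
|---|---|---|---|---|
| 2,900 | 16 | 2,900 × 0.16 = 464 | no | no |
| 5,000 | 16 | 5,000 × 0.16 = 800 | no | no |
| 15,900 | 15 | 15,900 × 0.15 = 2,385 | yes | no |

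The flagged count is 2,385 / 464 = 5.1 times the first unflagged count and 2,385 / 800 = 3.0 times the second.

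**Eosinophils.** 2,900 × 0.10 = 290/mm³ is flagged. 15,900 × 0.099 = 1,574/mm³ is not, and the leukocyte row is also silent. The unflagged count is 1,574 / 290 = 5.4 times the flagged one.

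**How wide the gap is.** A neutrophil count N escapes both rows when the white count is above 2,800 and below both N / 0.15 and 16,000:
- N = 500: white count below 500 / 0.15 = 3,333
- N = 1,000: white count below 6,667
- N = 1,500: white count below 10,000

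These values of N illustrate the arithmetic and are not proposed limits.

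**Where the gap ends.** At the lower end, 0.15 × 2,800 = 420. A count of 420/mm³ or less is always caught: with a white count of 2,800 or below the leukocyte row fires, and above 2,800 the share is under 15%. At the upper end, 0.15 × 16,000 = 2,400. A count of 2,400/mm³ meets the neutrophil row only at white counts of 16,000 or more, where the leukocyte row fires anyway. So backward ordering by the neutrophil row alone is confined to counts between 420 and 2,400/mm³.

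**Check at one white count.** At 5,000/mm³, a neutrophil count of 420 is 8.4% and is flagged; 2,400 is 48% and is not. For a fixed white count the row orders subjects correctly. The reversal arises only between subjects, or visits, with different white counts.

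**The case against.** The strongest reply is that this is a declared choice. The protocol names an external list in advance, applies it consistently and does not contradict itself. That stands: this is not an error against the plan's own terms. It explains the percentages but does not prevent a supplementary row.

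The second reply is that other parts of the plan would pick up a low count. Section 13.4.2 also plans summaries of raw hematology values, changes from baseline and normal-range shift tables. Section 11.1.2 requires any result that the investigator considers clinically significant to be recorded as an adverse event, which then enters the adverse event analysis. This is a real safeguard, with limits. Shift tables do not separate a slight fall below normal from a large one. Section 11.1.2 offers the same section 20.3 values as guidance, so the adverse event route is not fully independent of them. Neither route changes the notable-value proportions.

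Three stronger readings are tempting, and the documents do not support them:
- A reader might infer that neutrophil counts near 420/mm³ generally go unflagged and counts near 2,400/mm³ are generally flagged. These are corner cases. A count of 425/mm³ escapes only for white counts above 2,800 and below 2,833 (425 / 0.15).
- A reader might infer that dangerous counts are missed, harmless ones are flagged, and the comparison between arms is diluted. No section gives an absolute threshold that would justify either clinical label. In the flagged example, 85% of 15,900, or 13,515/mm³, are other white cells, so the differential is not shown to be unremarkable. Nothing allows an estimate of how many of the 150 subjects would be misclassified.
- A reader might infer that the table decides who continues in the study. Sections 6.3 and 20.2.4.2 leave that to the investigator, with the table as guidance only.

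**Conclusion.** The point holds as a cheap improvement to the safety analysis. The percentage-only limits make the neutrophil and eosinophil flags depend on the white count, and they can order absolute counts backwards: 464 or 800/mm³ can go unflagged while 2,385/mm³ is flagged, and 290/mm³ of eosinophils is flagged while 1,574/mm³ is not. The gap is not confined to the corners, since the 800/mm³ example arises at a white count of 5,000/mm³, well inside the leukocyte limits.

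The conclusion rests on reading the percentages as shares of the white count. The ratios of about five describe what the limits permit, not an expected error rate, and the effect on the between-arm comparison is unknown. The other planned displays reduce the consequence without removing it from the notable-value table.

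**What to change.** In the SAP, derive absolute neutrophils and absolute eosinophils as leukocytes × differential percentage / 100 at each visit, or use the laboratory's reported absolute counts if it supplies them. Report by arm the proportion of subjects beyond an absolute cut-off for each cell, placed next to the existing percentage rows. The sponsor should fix the cut-offs and write them down before unblinding. Keep the percentage rows, so that results remain comparable with the 1987 list.

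The new rows are meant for the analysis only. No cut-off value is suggested here, and whether the guidance on continued participation should change is left to the sponsor.

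The cost is two derived variables and two table rows, with no new blood samples because Table 5 already covers the inputs. Section 13.2 allows changes in statistical methods before database lock to be documented in the SAP without a protocol amendment. The downside is that the analysis supplements the 1987 list for two analytes, which should be stated in a table footnote.
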